Stress management interventions (SMI), non-pharmacological approaches to managing psychological and physical stress, show promise in reducing stress among nursing students. Although SMIs have demonstrated efficacy, more studies on senior students and Chinese student nurse interns are needed.

According to the transactional model of stress and coping proposed by Lazarus and Folkman, the three targets of effective stress management are stressors, coping strategies, and cognitive reappraisal. The stressor refers to any event or internal or external environmental stimulus that can be perceived

by an individual and elicit a positive or negative stress response; the coping strategy refers to the process by which an individual deals with internal or external demands that are perceived as stressful or exceed the resources of the individual; cognitive reappraisal is the method of changing an individual's evaluation of the stressor and self-defeating perception of stress.

Expressive writing (EW) is a form of writing therapy (WT) introduced by James Pennebaker in 1986. It enables individuals to express important emotional events they have experienced, to write down their deepest feelings and thoughts, and to find positive meaning in advert events. Following the transactional model of stress and coping, EW encompasses all three targets of stress reduction (using stressors as a writing topic, writing as a form of coping, and cognitive reappraisal during the writing process). At the same time, its simplicity, cost-effectiveness, brevity, and low expertise requirements make EW an easily accessible intervention method.

As there are few studies on the effectiveness of EW with student nurse interns, this study aims to investigate the efficacy of expressive writing in managing stress and work-related outcomes in student nurse interns, which may provide a valuable new approach.

2. Research Questions

- Is there any difference between the four repeated (at immediate, 4-week, 8-week, and 12-week follow-up) clinical practice stress tests between the intervention and control group in terms of the mean?
- Is there any difference between the four repeated (at immediate, 4-week, 8-week, and 12-week follow-up) coping strategy tests between the intervention and control group in terms of the mean of positive coping and negative coping?

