- Is there any difference between the four repeated (at immediate, 4-week, 8-week, and 12-week follow-up) work engagement tests between the intervention and control group in terms of the mean?
- Is there any difference between the four repeated (at immediate, 4-week, 8-week, and 12-week follow-up) perceived professional benefit tests between the intervention and control group in terms of the mean?

3. Research Objectives

General objective:

Evaluate the impact of expressive writing (EW) intervention on stress and work-related outcomes among Chinese student nursing interns

Specific objectives:

- To compare the effectiveness of EW (expressive writing) and NW (neutral writing) in managing clinical practice stress among student nurse interns between intervention and control groups at immediate and 4-week, 8-week, and 12-week follow-up.
- To compare the impact of EW and NW on improving coping strategies among student nurse interns between intervention and control groups at immediate and 4-week, 8-week, and 12-week follow-up.
- To evaluate the effectiveness of EW and NW in promoting work engagement between intervention and control groups at immediate and 4-week, 8-week, 12-week follow-up.
- To compare the impact of EW and NW on promoting perceived professional benefit among student nurse interns between intervention and control groups among student nurse interns at immediate and 4-week, 8-week, and 12-week follow-up.

4. Study Design

A randomized controlled trial with parallel design.

5. Inclusion and Exclusion Criteria of Participants

Inclusion criteria:

- Undergraduate student nurse interns in their first clinical internship (had no prior clinical practice experience)
- Have access and proficiency in utilizing social media
- Be able to read and write via the internet
- Be willing to fill in questionnaires and write according to the assigned writing prompts
- Never participated in an expressive writing or stress management intervention programs

Exclusion criteria:

- Intern at a self-contacted hospital
- Severe current psychological conditions
- Undergoing any form of psychotherapy
- With a habit of keeping diaries

Withdrawal criteria:

- Termination of internship for whatever reason
- Not submitting writing materials twice

6. Sample Size

Using the sample size formula for comparing the means of two independent samples of continuous variables to calculate the sample size.

$$n_i = 2 \left(\frac{Z_{1-\alpha/2} + Z_{1-\beta}}{ES} \right)^2$$

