$$ES = \frac{|\mu_1 - \mu_2|}{\sigma}$$

To detect between-group differences with an effect size of 0.69 in clinical practice stress by Stress Rating Scale for Nursing Students in Practice after 10 weeks of intervention (primary outcome), with an α level of 0.05, we require 33 participants per group to attain a power of 80%. Accounting for an expected 10% loss to follow-up, we should include 74 participants.

7. Sampling and Grouping

All eligible student nurse interns in the four target hospitals constituted the sampling frame. Two of the four target hospitals will be selected by lottery and the intervention and control groups will be determined by a coin toss.

Participants will be sampled for both the intervention and control groups using the following method: all potential participants were entered alphabetically into Column A of the Excel sheet from A to Z. Then, random numbers will be generated in column B of the Excel sheet using the Rand() function. The 37 participants with small random numbers will be included as study participants in both groups.

A research assistant who will not be involved in other parts of the study completed all the above processes.

8. Blinding

This is a single-blinded randomized controlled study.

The intervention trainer will not be blinded, given that a single researcher conducts the study. To minimize experimenter bias, outcome assessments will be conducted through an online questionnaire survey platform (Wenjuanxing), with the trainer distributing the same link to all participants. During data

collection, only acronyms of the questionnaires will be used to avoid self-fulfilling expectations.

Participants will be informed during the recruitment phase only that the study aimed to explore the effect of writing on internship experience and feelings. Assignment to the intervention or control group will remain undisclosed to participants until the end of the 3-month follow-up.

Participants could unblind themselves by exiting the study and requesting debrief information.

9. Intervention Description

Intervention group:

According to the writing prompts, online expressive writing focuses on stressful events and will be conducted twice a week (every Monday and Thursday) for 15 minutes each time, lasting for ten weeks.

Writing prompts are developed based on Emotional Processing Theory (EPT) and Cognitive Adaptation Theory (CAT).

- 1st writing/Monday:

[figure not shown]

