- 2nd writing/Thursday:

Describe the specified object in the picture (from week one to week ten, provide pictures of the door, hairstyle, pants, room, hands, shoes, view from a window, clothes, water bottle, and computer).

In your writing, concentrate on the facts and details of the activity and thing you chose. We are not interested in your emotions or opinions, rather we want you to try to be completely objective. Feel free to be as detailed as possible.

To ensure the effectiveness of online writing, we developed a webpage suitable for the program. Participants can write from their computers or mobile devices. When a participant goes to the web page, the first page will be the instructions. This page shown before the writing tasks described the main objective of each task, emphasizing the importance of carefully reading the instructions. After reading the instructions, participants fill in their unique number and click on the "start writing" button. Then it will turn to the second

page for writing. There will be a countdown clock on this page, with the remaining time for the task. The clock flashed when one minute remained. When the time expires, the writing page will automatically close and display the final text. At this point, no editing was possible, but participants could read their texts.

10. Outcome Measures

All measures will be taken one day before the start of the intervention, one day after the end of the intervention, and followed up at 4 weeks, 8 weeks, and 12 weeks after the end of the intervention.

Primary outcome: Clinical Practice Stress

Stress Rating Scale for Nursing Students in Practice

The scale consists of 6 dimensions and 37 entries, including the nature of work, workload, preparation for an internship, interpersonal relationships, work support, and learning and work impulse. The scale rates on a 4-point Likert scale, with no stress, mild stress, moderate stress, and severe stress, assigned a score of 0, 1, 2, and 3, respectively, and the higher the score, the greater the stress.

Secondary outcome: Coping Strategy, Work Engagement, Perceived Professional Benefit

Brief Coping Style Scale

The scale consists of two dimensions, positive and negative coping, with 20 entries. A 4-point Likert scale is used, with 1-4 indicating "not used" to "often used". Positive coping has 12 entries, and negative coping has 8 entries, with higher scores indicating more frequent use of coping strategies.

Utrecht Work Engagement Scale

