The scale consists of 3 dimensions: vitality, dedication, and concentration, comprising 15 entries. A 7-point Likert scale is used, with scores ranging from 0-6 for "never," "almost never," "rarely," "sometimes," "often," "frequently," and "always." The total score is the sum of the scores of each entry. An average entry score of 4 or more is defined as a high level of work engagement, 2-4 as a moderate level, and less than 2 as a low level of work engagement.

Perceived Professional Benefits Scale

The scale consists of 7 items of positive career sense, 6 items of good nurse-patient relationship, 6 items of sense of belonging to the team, 8 items of self-growth, and 6 items of identification with friends and relatives, 33 items in 5 dimensions in total, and each item is scored 1 to 5 on a 5-point Likert scale ranging from "strongly disagree" to "strongly agree. The higher the score, the stronger the perceived professional benefit.

11. Data Analysis

Data will be analyzed with Stata version 14. All endpoints will be analyzed with generalized estimating equations and will use robust standard errors. The working correlation structure will be specified as exchangeable.

Data from all available time points will be used. The independent variables included in the model will be the treatment group (categorical) and the baseline value of the dependent variable (continuous). A model that additionally adjusted for age and sex for the primary endpoint will run.

The primary endpoint and secondary endpoints will all be analyzed with an intention-to-treat approach.

References

Ahmad, T. B., & Meltem Meriç, R. (2021). The effect of an online psychoeducational stress management program on international students'

ability to cope and adapt. *Perspectives in Psychiatric Care*, 57(4), 1673-1684. doi:10.1111/ppc.12735

Aloufi, M. A., Jarden, R. J., Gerdtz, M. F., & Kapp, S. (2021). Reducing stress, anxiety, and depression in undergraduate nursing students: Systematic review. *Nurse Education Today*, 102, 104877. doi:10.1016/j.nedt.2021.104877

Aslan, H., & Pekince, H. (2021). Nursing students' views on the COVID-19 pandemic and their perceived stress levels. *Perspectives in Psychiatric Care*, 57(2), 695-701. doi:10.1111/ppc.12597

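### The GEE has no visit or group-by-visit term, so it estimates one visit-averaged effect, not the per-visit comparisons in the objectives or the end-of-intervention difference behind the sample size

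*Protocol*

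**What the plan says.** Section 11 (Data Analysis) specifies generalized estimating equations with an exchangeable working correlation and robust standard errors for all endpoints. On the data it says: "Data from all available time points will be used". On the terms: "The independent variables included in the model will be the treatment group (categorical) and the baseline value of the dependent variable (continuous". The only other model is for the primary endpoint: "A model that additionally adjusted for age and sex for the primary endpoint will run". The protocol mentions no visit term, group-by-visit term or per-visit contrast.

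Section 10 (Outcome Measures) schedules one baseline and four post-baseline assessments, the latter "one day after the end of the intervention, and followed up at 4 weeks, 8 weeks, and 12 weeks" after it.

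Section 3 (Research Objectives) sets the first specific objective as comparing how the two kinds of writing perform "in managing clinical practice stress among student nurse interns between intervention and control groups at immediate and 4-week, 8-week, and 12-week follow-up". The other three objectives name the same four times for coping, engagement and professional benefit.

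Section 6 (Sample Size) uses the formula for two independent means. The assumed standardised difference is 0.69, and its outcome and timing are given as follows: "in clinical practice stress by Stress Rating Scale for Nursing Students in Practice after 10 weeks of intervention (primary outcome".

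**The concern.** Because the scores from all visits enter one model and group appears only as a main effect, there is one group coefficient. It summarises the immediate, 4-, 8- and 12-week differences in one number and estimates none of them separately. The objectives ask for each, and the sample size was derived for one of them.

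Two things are at stake. The trial could not report the effect it was sized to detect. It also could not say whether an effect lasts, which is what the three later visits are able to show. Because the regressors are listed explicitly, a later analysis plan would have to change the stated model rather than fill in detail.

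**Working it through.** **Inputs from the protocol.** Effect size 0.69, two-sided α = 0.05, 80% power, 33 per arm, 10% loss, 74 in total (Section 6); four post-baseline visits (Section 10); model terms (Section 11).

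**Assumptions, because the protocol gives no figures.** SD 1; the same correlation r between all pairs of visits, baseline included, with r = 0.6 and a range of 0.3 to 0.8; complete data; no hospital effect; normal approximation. The time courses are illustrations.

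**1. The protocol's own figure.** n = 2 × ((1.96 + 0.84)/0.69)² = 33.0 per arm. With 10% loss, 33/0.9 = 36.7, so 37 per arm and 74 in total. This reproduces Section 6. It is a comparison of two means at one time point, with no repeated-measures term.

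**2. What the stated model estimates.** With complete data and exchangeable correlation, the group coefficient is the plain mean of the four visit differences.

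- Linear fade: (0.69 + 0.46 + 0.23 + 0)/4 = 0.345 SD
- Late onset: (0 + 0.23 + 0.46 + 0.69)/4 = 0.345 SD
- Fade to half by week 12: (0.69 + 0.575 + 0.46 + 0.345)/4 = 0.5175 SD
- Constant: 0.69 SD

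The first two share a coefficient, although their end-of-intervention effects are 0.69 and 0.

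**3. Precision.** After baseline adjustment, the variance is 1 − r² for a single visit and (1 + 3r)/4 − r² for the four-visit mean. The SE of the group difference is √(2 × variance/33).

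At r = 0.6:
- single visit: variance 0.64, SE 0.197, 95% half-width 0.39 SD
- average: variance 0.34, SE 0.144, 95% half-width 0.28 SD
- ratio of widths 1.37 (1.54 at r = 0.3; 1.31 at r = 0.8)

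**4. Power with 33 per arm** at r = 0.6, with the range over r = 0.3 to 0.8 in brackets:

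| Time course | Average effect | Power, average | Power, immediate contrast |
|---|---|---|---|
| Constant 0.69 | 0.69 | 99.8% (99.4–100%) | 94% (84–99.7%) |
| Fade to half | 0.52 | 95% (92–99.6%) | 94% (84–99.7%) |
| Fade to 0 | 0.345 | 67% (61–86%) | 94% (84–99.7%) |
| Late onset | 0.345 | 67% (61–86%) | 5% (no effect at that visit) |

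The smallest average detectable with 80% power is 2.80 × 0.144 = 0.40 SD at r = 0.6 (0.32 to 0.43 SD over the range).

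**5. Simulation check.** Exchangeable GEE with robust SE, complete data, r = 0.6, 4,000 simulated trials per time course; sizes of coefficients:
- Fade to 0: the stated model returned 0.346 (rejection 69%); the group-by-visit model returned 0.689 at the immediate visit (94%).
- Late onset: 0.345 (68%) and 0.003 (5.8%).
- Constant effect: rejection 99.6% for the average and 94.3% for the immediate contrast.

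**The case against.** **The research questions fit the stated model.** Section 2 asks "Is there any difference between the four repeated (at immediate, 4-week, 8-week, and 12-week follow-up) clinical practice stress tests" in terms of the mean, and one coefficient over four repeated measures can answer that. This stands for Section 2. It does not reconcile Section 11 with the objectives, which name each visit.

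**The sample-size wording can be read more widely.** All four post-baseline visits fall after ten weeks of writing, and the label of primary outcome may refer only to the stress scale, since Section 10 names the scale without a visit. The protocol does not say outright that the immediate assessment was powered. It remains the more natural reading: the intervention lasts ten weeks, the first assessment follows one day later, and the formula is for a single comparison.

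**The average is a legitimate estimand and can be the stronger one.** This is correct. It has more power under a constant effect and about equal power under a fade to half. Power falls below 80% only under assumed time courses such as full fade or late onset.

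**The equal averages need complete data.** Also correct. If 10% of each arm leave after the first post-baseline visit, at r = 0.6 the coefficient becomes a weighted average: 0.364 SD for the fade and 0.326 SD for late onset. A gap of 0.04 SD is far below the SE of 0.144, so the two remain indistinguishable in practice.

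**More contrasts bring multiplicity.** Four visits for five scores (stress, two coping scores, engagement, benefit) make 20 contrasts. Naming one primary contrast settles this for the primary outcome; the others should be labelled secondary.

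**Hospital is confounded with arm.** Section 7 selects two hospitals, and "the intervention and control groups will be determined by a coin toss". Per-visit contrasts share that confounding with the average. This is a separate flaw, which the present change does not address.

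**Conclusion.** The concern holds and should be fixed. The model in Section 11 cannot deliver the visit comparisons in Section 3, and on the natural reading of Section 6 it does not test the quantity that was powered. That follows from the listed terms and needs no numerical assumption.

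The size of the consequence does depend on assumptions. If the effect fades to 0, the model targets half of the planned 0.69 SD, with 67% power at r = 0.6 (61–86%). If the effect is constant, nothing is lost in power. No error in N = 74 is shown. The power figures rest on equal correlations, complete data and no hospital effect, none of which the protocol states.

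**What to change.** In Section 11, model the four post-baseline scores on group, visit (categorical), group × visit and baseline score. Keep the exchangeable GEE with robust SE, and report the group contrast at each of the four visits. Then make the primary estimate and Section 6 agree by one of two routes:

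1. Name the immediate post-intervention contrast as primary, which matches Section 6, and keep the four-visit average as a supportive summary.
2. Declare the four-visit average primary, restate the power basis for it (33 per arm gives 80% power for about 0.40 SD at r = 0.6), and still report the visit contrasts.

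Either route should state that the remaining contrasts are secondary.

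The cost is two or three sentences and no new data. Route 1 gives up precision if the effect is constant: the primary interval is 37% wider at r = 0.6 (31–54% wider for r from 0.8 to 0.3). Under the protocol's own individual-level assumptions the immediate contrast keeps at least the stated 80% power, but that does not cover hospital effects. The simulated rejection rate of 5.8% when the immediate effect is null suggests that robust SEs may be slightly too small at 33 per arm, which also deserves attention when the text is revised.
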